### 5.5. Summary of Nonclinical and Clinical Trials

#### 5.5.1. Nonclinical Studies

#### 5.5.1.1. Toxicology Testing

FDP is assumed to be active on a species-species basis. Human plasma may cause severe toxicity reactions in animals and is not tolerated at dosages approaching those generally used in humans. Routine toxicology testing in laboratory animals is not considered to contribute any relevant information for the safety and efficacy of FDP in clinical use.

#### 5.5.1.2. Pharmacology

HemCon Medical Technologies, Inc. developed lyophilized swine plasma which was compared with swine FFP in a coagulopathic, multi-trauma swine model (Spoerke et al-2009). Anesthetized, instrumented female pigs (n=32) were studied under conditions of femur fracture, 60% hemorrhage, 30-minute shock period, hypothermia, and Grade 5 liver injury. Clotting factor activity was decreased by an average of 14% in lyophilized swine plasma as determined by preand post-lyophilization measurements. Acute blood loss, survival, and heart rate were similar among all groups. Swine resuscitated with lyophilized swine plasma had equivalent or higher mean arterial pressure than those treated with FFP. Both lyophilized swine plasma and FFP, either in combination with RBCs (1:1) or alone, were similar in restoring standard coagulation function: prothrombin time (PT), aPTT, fibrinogen, and thromboelastogram tracings, to baseline values in this dilutional, coagulopathic, poly-trauma swine model. In conclusion, lyophilized swine plasma demonstrated equivalent efficacy to FFP in this swine resuscitation model.

#### 5.5.2. Clinical Studies

Lyophilized, pooled human plasma was used extensively in World War II for resuscitation, but its use was discontinued during the 1950s due to transmission of HBV. In the mid-1980s, the Thai Red Cross undertook a large-scale effort to produce LyP from single units of plasma for use in rural hospitals to meet the need for availability of blood products (Isarangkura et al-1987). Since that time, only the German Red Cross and French Military have developed LyP products, and the use has been limited to the European Union and in theater in places such as Iraq or Afghanistan. Information about the current use of the French LyP product in Iraq and Afghanistan by U.S. Forces is largely anecdotal and clinical studies on the product were not conducted prior to introduction in those settings. Currently, United States Special Operations Command (SOCOM) is working under a special Expanded Access Investigational New Drug (IND) application that approves a joint venture between SOCOM and the French Military at the Centre de Transfusion Sanguine des Armées. This Expanded Access IND allows for the use of a French-developed FDP product in theater in Iraq and Afghanistan. The French-developed FDP has been approved by the French Ministry of Health, but has not been approved by the FDA (Enterprise Information Technology (eIT)-2014).

#### **5.5.2.1.** Toxicology in Humans

Based on dried plasma use in World War II and the recent human clinical studies of FDP performed by HemCon Medical Technologies, Inc., there is evidence to suggest that the toxicology of FDP when infused into humans is similar to that of FFP.

It is important to note that RePlasTM FDP has similar levels of citrate compared to FFP. Although, this FDP product, RePlasTM has never been infused into humans, there is considerable information in the literature on the effects of citrate after transfusion of blood products. The additional citric acid in FFP has the potential to slightly increase the risk for citrate toxicity, a risk that is already present and well described in the literature for infusion of large volumes of blood products (Klein and Anstee-2005, Silberman et al-2009).

Harmful effects of citrate infusion may occur if the dosage exceeds 250 mg/kg/hour. Citrate anticoagulant is present in blood or plasma collected and stored for transfusion, and rapid rate of infusion of blood (30 mL/kg/hour) can lead to a decrease in ionized calcium, known as citrate intoxication (Dart-2004). Uncorrected citrate intoxication and the insufficient ionized calcium that ensues can lead to cardiac dysrhythmia, cardiac arrest, tetany, or seizures.

#### 5.5.2.2. Pharmacokinetics and Biological Disposition

The pharmacokinetics and biological disposition of FDP are expected to be the same as FFP.

# 5.6. Known and Potential Risks and Benefits to Human Subjects

#### 5.6.1. Risks/Discomfort to Subjects and Precautions to Minimize Risk

Outlined below are anticipated and unexpected adverse reactions (ARs), and a brief description of procedures to ameliorate risks and symptoms. All known risks and precautions described here are explained in detail in the informed consent.

#### **5.6.1.1.** Venipuncture

Donation of blood and blood products and the collection of blood samples for laboratory testing carries minimal risk of minor discomfort and the possibility of pain/soreness, minor bruising, discoloration, swelling, at the site of the needle puncture and, rarely, the possibility of infection at the needle puncture site.

#### 5.6.1.2. Whole Blood Collection Reactions

Side effects of WB collection include:

- Complications such as a hematoma, redness, nerve damage, arterial puncture, or localized infection at the venipuncture site; and
- Nausea, unpleasant taste, vomiting, light-headedness, fainting, malaise, or seizures.

#### 5.6.1.3. Plasmapheresis Reactions

Side effects of plasmapheresis include:

• Blood loss from the inability to return RBCs during automated plasmapheresis, which may result in:

- Termination of the procedure; and
- Deferral from donation for 8 weeks (21 Code of Federal Regulations (CFR) 640.63(e)).
- Complications such as a hematoma or localized infection at the venipuncture site;
- Tingling of lips or fingers or muscle cramping, spasms seizures, tetany, cardiac arrhythmia due to the citrate anticoagulant used in an automated plasmapheresis procedure;
- Allergic reactions such as flushing, itching, hives, abdominal cramps, difficulty breathing, chest pain, or bronchospasm, which may vary in severity from mild to lifethreatening;
- Nausea, unpleasant taste, vomiting, light-headedness, fainting, malaise, or seizures; and
- Any other adverse reaction specified by the manufacturer of the automated collection device in its operator's manual or instructions for use.

#### **5.6.1.4.** Local Reactions and Systemic Infusion Reactions

Known potential risks associated with allogeneic FFP infusion are well described in the literature. The known risks of FDP infusion are unknown but they are expected to be similar to those associated with the use of FFP. Some of these risks are mitigated by the use of autologous plasma in this study. Subjects receiving FDP are to be monitored during administration and up to 7 days post-infusion for AEs. The expected risks of FDP infusion include:

- Pain at venipuncture site and other venipuncture related ARs;
- Tingling of lips or fingers, muscle cramping, spasms, seizures, or cardiac arrhythmia due to the citrate anticoagulant used during plasma collection;
- Allergic reactions such as flushing, itching, hives, abdominal cramps, difficulty breathing, chest pain, or bronchospasm, which may vary in severity from mild to life-threatening;
- Nausea, unpleasant taste, vomiting, light-headedness, fainting, malaise, or seizures;
- Non-immunologic complications such as the transmission of infectious agents, bacterial sepsis, transfusion-associated circulatory overload, hypothermia-cardiac arrhythmias;
- Metabolic complications such as citrate toxicity-hypocalcemia, acidosis, alkalosis, hyper- or-hypokalemia, and coagulopathies; and
- Hyperventilation.

Other rare side effects that have occurred in patients receiving (1) non-autologous plasma therapy or (2) excess fluid, including their own plasma include:

- Lowered immunity;
- Heart failure;

- Fluid in the lungs causing breathing difficulty;
- Stroke or death;
- Swelling of feet or hands;
- Increase in blood pressure;
- Fever;
- Back pain;
- Redness of urine; and
- Kidney failure.

#### 5.6.1.5. Pregnancy

Risks to unborn babies are unknown at this time; pregnant females will be excluded from this study. Study subjects should not become pregnant for at least 3 months after the last infusion of FDP.

#### **5.6.1.6.** Lactation

Risks to nursing infants are unknown at this time; breastfeeding and lactating females will be excluded from this study.

#### 5.6.1.7. Allergic Reaction

As with any IND product administration and no matter what precautions are taken, there is always the risk of a serious, or even life-threatening, allergic reaction. Medical emergency equipment is at the site to handle emergencies, such as anaphylaxis, angioedema, bronchospasm, and laryngospasm.

#### 5.6.1.8. Unknown Risks

Furthermore, as with all research there is the remote possibility of risks that are unknown or that cannot be foreseen based on information that is currently available.

#### 5.6.2. Alternatives to this Investigational New Drug Product or Study

An alternative is to not participate in this study.

#### 5.6.3. Intended Benefit for Subjects

There is no guaranteed benefit for study subjects other than any sense of satisfaction accruing from their contribution to medical science.

# 5.6.4. Risks to the Study Personnel and the Environment

The principal risks to study personnel involved in this trial are the same as those found in a day-to-day clinical setting (i.e., handling of needles that may be contaminated and the attendant risks including hepatitis, HIV, and other human pathogens). Adherence to standard operating procedures (SOPs) for working with infectious agents and universal precautions will reduce the risk of exposure.

There are no known risks to the environment other than those associated with the generation of biohazardous waste attendant to infusion of humans. All biohazardous waste will be disposed of as stipulated by local, state, and Federal regulations and in accordance with study site SOPs.

# 5.7. Route of Administration, Dosage Regimen, Treatment Period, and Justification

In this safety study, 3 cohorts of healthy subjects will receive an intravenous (IV) infusion of FDP and/or FFP as follows:

- **Cohort 1:** Eight enrolled subjects will each receive a 1 unit (approximately 270 mL) dose of FDP:
  - Arm 1 subjects will receive 1 unit (approximately 270 mL) of autologous FDP manufactured from WB. These subjects are expected to make one WB donation. Subjects with a low-volume donation (< 450 mL) may be withdrawn from the study. The site will discard the low-volume donation per their SOP for handling blood and blood products.

  - Arm 2 subjects will receive 1 unit (approximately 270 mL) of autologous FDP manufactured from plasmapheresis collected FFP. These subjects are expected to undergo one plasmapheresis session. Subjects with a low volume donation (< 500 mL) may be withdrawn from the study. The site will discard the low-volume donation per their SOP for handling blood and blood products.

- Cohort 2: Eight enrolled subjects will each receive 2 units (approximately 540 mL) of FDP:
  - Arm 3 subjects will receive 2 units (approximately 540 mL) of autologous FDP manufactured from WB. These subjects are expected to make two WB donations that are scheduled a minimum of 28-days apart. Subjects with a low-volume donation (< 450 mL) may be withdrawn from the study. The site will discard the low-volume donation per their SOP for handling blood and blood products.

  - Arm 4 subjects will receive 2 units (approximately 540 mL) of autologous FDP manufactured from plasmapheresis collected FFP. These subjects are expected to undergo one plasmapheresis session. Subjects with a low-volume donation (< 500 mL) may be withdrawn from the study. The site will discard the low-volume donation per their SOP for handling blood and blood products.
    - Should an Arm 4 subject require a second plasmapheresis collection attempt, to ensure subject safety, serum protein electrophoresis (SPEP) and STAT total protein will be performed just prior to the subsequent plasmapheresis. If any abnormalities are detected, the subject will be referred to a physician, scheduled for early withdrawal, and replaced with another subject.
- Cohort 3: Eight subjects will each receive 2 separate infusion treatments, each dosed at approximately 810 mL. One 810 mL infusion will be with 3 units of autologous FDP and the other approximately 810 mL infusion will be with 3 units of autologous control plasma (FFP). Cohort 3 subjects will be randomized to a product treatment sequence indicating whether their first infusion will be FDP (Arm 5) or FFP (Arm 6).

The starting material for the manufacture of all Cohort 3 FDP units and FFP units will be from autologous plasmapheresis.

- Arm 5 subjects will receive FDP at their first infusion and FFP at their second infusion; infusion treatments will be separated by a 2-week interval; and
- Arm 6 subjects will receive FFP at their first infusion and FDP at their second infusion; infusion treatments will be separated by a 2-week interval.

All subjects in Cohort 3 are expected to undergo 3 to 4 plasmapheresis sessions that are each separated by a minimum of 1 week. Subjects who do not meet the minimum volume requirement during plasmapheresis (≥500 mL) may be withdrawn from the study. Low volume collections (< 500 mL) will be discarded per the clinical site's SOP for handling blood and blood products.

As a measure of donor safety, SPEP will be performed on all subjects undergoing the procedure, regardless of assigned cohort/treatment arm. If any abnormalities are detected, the subject will be referred to a physician, scheduled for early withdrawal, and replaced with another subject.

For subjects undergoing multiple plasmapheresis collections, total protein measured by a Beckman Coulter AU analyzer will be performed STAT or up to 24 hours prior to initiating the plasmapheresis. Total protein will only be performed at subsequent plasmapheresis sessions, not during the first collection.

# **5.8.** Compliance Statement

The study will be conducted according to the protocol and in compliance with FDA International Conference on Harmonization (ICH) Good Clinical Practice (GCP), Belmont Principles, and other applicable regulatory and Department of Defense (DoD) requirements. All identified study personnel will be trained to perform their roles and will carry out their responsibilities in accordance with FDA, ICH GCP guidelines, and study site's SOPs. Roles and responsibilities of study staff are presented in Appendix A.

# 5.9. Study Population

Male and female healthy volunteers who are eligible for WB donation or plasmapheresis donation based on FDA regulations and the AABB donor history questionnaire will be included in this study. Subjects whose only reason for exclusion according to the AABB donor history questionnaire is travel deferral will be accepted. A sample of the complete AABB donor history questionnaire is presented in Appendix B. In addition to the eligibility criteria indicated by the questionnaire, potential subjects must also meet the Inclusion/Exclusion criteria as previously mentioned and later referred to in section 7.4 and section 7.5.

Refer to section 11.2 for a statistical justification of the sample size.

#### 5.10. Study Site

The Hoxworth Blood Center (HBC) is an academic blood center that provides daily blood and cell therapy product needs to the whole community of the Greater Cincinnati area which is populated by approximately 1.9 million inhabitants. Cincinnati is located in Southwestern Ohio and is highly diverse with a population mostly composed of European (German, Irish, Italian,

and Jewish) and African background inhabitants. HBC processes approximately 80,000 blood units a year and approximately 10,000 platelets apheresis a year. It routinely produces plasma products from WB and plasmapheresis procedures for the community and provides immunohematology reference laboratory services and transplantation immunology services for the Greater Cincinnati area hospitals. The HBC/University of Cincinnati research program is extremely active in the development and validation of innovative products in transfusion medicine and cell therapies. The center is located central to the University Medical campus, at a 1 to 5 minute walking distance to the major hospitals and facilities of the University. The HBC has the personnel, expertise, and equipment necessary to perform this study, including blood donation staff, plasmapheresis devices, expert nurses in the field of plasmapheresis, and on-call doctor. The work is supervised and directed by [name], MD, PhD, who is Professor of Pediatrics and Deputy Director of the Blood Center, and who will be in charge of the medical aspects of the study. The HBC is uniquely qualified given its long-term experience in the development of clinical research trials in blood banking involving healthy volunteers and collection/infusion of large amounts of blood derived cell/plasma products.

#### 6. TRIAL OBJECTIVES AND PURPOSE

## 6.1. Primary Objective

The primary objective of this study is to assess the safety of single infusions with the RePlasTM FDP product at increasing fixed doses of either 1 unit (approximately 270 mL), 2 units (approximately 540 mL), or 3 units (approximately 810 mL) in normal healthy subjects. In the 2 lower dose cohorts, safety will also be assessed in terms of the type of autologous plasma used as the starting material in the manufacture of the investigational product:

- FDP derived from WB where CPD was used as the anticoagulant, or FDP-CPD; and
- FDP collected by plasmapheresis where ACD was used as the anticoagulant, or FDP-ACD.

The highest dose cohort will receive FDP manufactured only from FFP collected by plasmapheresis (FDP-ACD). Conclusions on whether the study meets its safety objectives will be based only on treatment emergent adverse events (TEAEs). These are adverse events (AEs) that occur after treatment (plasma infusion) has begun and throughout the study's post-infusion follow-up period.

# 6.2. Secondary Objectives

The secondary objectives are to:

- Assess the safety of a fixed-dose infusion of 3 FDP units (approximately 810 mL) in comparison to infusion with the same dose of autologous FFP collected during plasmapheresis; and
- Determine if the changes in specific coagulation factors, hematology, and chemistry values are similar within clinically meaningful levels after infusion of either 3 units of autologous FDP or FFP.

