## 11.1.2.2. Exploratory Analyses Comparing FDP to FFP (Secondary Objective 2)

The analyses conducted for secondary objective 1 will be used to meet secondary objective 2. In addition, descriptive statistics on a post-infusion, abnormal coagulation function assay that is greater than a 20% change in either direction from baseline for PT/INR and/or aPTT values will be presented using separate shift tables. Shift tables based on the upper limit of normal (ULN) will also be provided for D-dimer, PF 1+2, TAT, and C3a des Arg.

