# 11.3. Level of Significance

The level of significance does not apply since no statistical testing will be done in this study.

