1.2.2 Secondary Objectives (Cohort 3 Only)

The secondary objectives are to:

- Assess the safety of fixed-dose infusion with three autologous FDP units (approximately 810 mL) in comparison to fixed-dose infusion with the same dose of autologous FFP collected during plasmapheresis; and
- Determine if the changes in specific coagulation factors, hematology, and chemistry values are similar within clinically meaningful levels after infusion of three units of either autologous FDP or FFP.

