4.5 Statistical Methods and Analysis

4.5.1 Overview and General Plans

This section describes the analytic approach for addressing each of the study's objectives by the defined primary and secondary endpoints. The analysis will be descriptive and consist of frequencies and percentages for categorical measures and the number of subjects, mean, standard deviation, median, minimum, maximum, 25th and 75th percentile for continuous measures as appropriate. Descriptive statistics will be summarized for each treatment group. SAS Version 9.3 or higher (SAS Institute Inc., Cary, NC) will be used to perform all statistical analyses.

Modeling

Modeling is not incorporated in the SAP since it is not required to meet the primary or secondary objectives.

Multiplicity Issues

Not powered to test for treatment group differences; no adjustment for multiple testing is planned for the study analyses.

Project Center Effects

This is a single-site study. Adjustment for project center effects will not be performed.

Interim Analysis

No interim analyses are planned for this study.

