4.5.4 Conduct Exploratory Analyses Comparing FDP-ACD to FFP (Secondary Objective #2)

The analyses conducted for secondary objective #1 will be used to meet secondary objective #2. In addition, descriptive statistics on a post-infusion, abnormal coagulation function assay, which is greater than a 20% change in either direction from baseline for PT/INR and/or aPTT values, will be presented using separate shift tables. Shift tables based on the upper limit of normal (ULN) will also be provided for D-dimer, prothrombin fragment (PF) 1+2, thrombin-antithrombin complex (TAT) and C3a des Arg.

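### Secondary objective 2 calls for a judgement on FDP–FFP similarity, but the plan sets no between-product limit and reports no within-subject difference or interval to base it on

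*Protocol*

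**What the plan says.** Protocol 6.2 sets the objective to "Determine if the changes in specific coagulation factors, hematology, and chemistry values are similar within clinically meaningful levels". SAP 1.2.2 repeats it, asking whether the changes "are similar within clinically meaningful levels after infusion of three units of either autologous FDP or FFP". The second endpoint in protocol 6.4.2 uses the same language for hematology, urinalysis, vital signs, DAT and chemistry. No level is given in any of these places.

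The analysis is in protocol 11.1.2.2 and the SAP section headed Secondary Objective #2 (the second one numbered 4.5.4). The protocol states: "The analyses conducted for secondary objective 1 will be used to meet secondary objective 2". The SAP says the same: "The analyses conducted for secondary objective #1 will be used to meet secondary objective #2". Two additions follow in the protocol, mirrored in the SAP. Abnormal coagulation results with a "greater than a 20% change in either direction from baseline for PT/INR and/or aPTT values will be presented using separate shift tables". Then: "Shift tables based on the upper limit of normal (ULN) will also be provided for D-dimer, PF 1+2, TAT, and C3a des Arg".

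SAP 4.5.1 limits continuous measures to counts, means, SDs, medians, ranges and quartiles, leaves out modeling, and adds: "Not powered to test for treatment group differences; no adjustment for multiple testing is planned for the study analyses". Protocol 11.3 states: "The level of significance does not apply since no statistical testing will be done in this study".

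**The concern.** The objective asks a question with a yes or no answer: are the changes close enough not to matter clinically? Answering it needs a limit on the FDP–FFP difference and an estimate of that difference with its uncertainty. The plan provides neither, so whoever writes the final report must judge similarity by eye.

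This matters because Cohort 3 is the trial's only controlled comparison and its results go into the report sent to the FDA (protocol 10.6.6). Protocol 5.3 already cites a 16-subject study of another lyophilized plasma as showing no relevant clinical difference from FFP, so statements of this kind do get carried forward. A real difference is not far-fetched: protocol 5.5.1.2 reports an average 14% fall in clotting factor activity when swine plasma was lyophilized.

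**Working it through.** **1. The plan's own precision figure.** Protocol Table 16 (SAP Table 3) gives a 95% Clopper-Pearson interval of 1.6–29.2% for 10% incidence in 24 subjects. With x = 24 × 0.10 = 2.4, the limits are the 2.5% quantile of Beta(2.4, 22.6) and the 97.5% quantile of Beta(3.4, 21.6). These are 1.6% and 29.2%, width 27.6, as stated; all nine cells of the table reproduce. The table concerns adverse event incidence. Nothing comparable exists for objective 2.

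**2. What each planned threshold compares.**

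| Threshold | Applies to | Compares |
|---|---|---|
| 20% change | PT, INR, aPTT | Post- with pre-infusion value, same infusion |
| 0.5 ug/mL FEU (SAP Table 11 note) | D-dimer | One value with a cut-off |
| ULN shift | PF 1+2, TAT, C3a des Arg | One value with the normal range |
| Above-ULN row (SAP Table 9 shell) | Measures in Table 9 | One value with the normal range |

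None compares FDP with FFP.

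**3. What each output shows for Cohort 3.**
- Table 9 is produced separately for infusion #1 and infusion #2. Within one table, FDP and FFP columns hold 4 and 4 different subjects.
- Table 12 is by sequence and period. Its Total pools both sequences within a period, so it mixes the products.
- Figure 4 overlays individual lines colored by product for 19 coagulation measures.

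No shell has a column for FDP minus FFP within subject, or an interval.

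**4. Why the planned summaries cannot supply the interval.** Write m(s,p) for the mean change in sequence s and period p. Sequence 1 is FDP then FFP. The period-adjusted estimate is

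½ × {[m(1,1) − m(1,2)] + [m(2,2) − m(2,1)]}.

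Its point value can be built from Table 12 cell means. Its standard error is SDd/√8 (4 subjects per sequence, 6 df), where SDd is the SD of the within-subject difference. If both products have SD s and within-subject correlation r, SDd = s√[2(1 − r)]. The tables give s but not r. Taking r as 0, 0.5 and 0.8 (assumed), SDd is 1.41s, 1.00s and 0.63s.

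**5. Precision available with 8 subjects.**
- 90%: t(0.95, 6)/√8 = 1.943/2.828 = 0.687 SDd.
- 95%: t(0.975, 6)/√8 = 2.447/2.828 = 0.865 SDd.
- For contrast, 4 versus 4 as Table 9 is laid out, 95%: 2.447 × √(2/4) = 1.73 times the between-subject SD of the change.

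SDd is not in the documents. For assumed values of 10, 20 and 30 percentage points, the 90% half-widths are 6.9, 13.7 and 20.6, and the 95% half-widths 8.7, 17.3 and 26.0.

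**6. If a limit were recorded.** Suppose similarity is stated only when the 90% CI lies inside the limit. With truly identical products and 6 df, that happens 99.9%, 90%, 61% and 34% of the time when SDd is 0.5, 0.75, 1.0 and 1.25 times the limit. An 80% chance needs a limit of about 1.18 SDd.

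**The case against.** The best defence is that this is a 24-subject, first-in-human Phase 1 study. Both documents label the section exploratory, plan no hypotheses or tests, and say openly that the study is not powered for product differences. A descriptive comparison is legitimate there. The plan also offers more than means: quartiles, ranges, above-ULN counts, shift tables, sequence-by-period summaries and individual plots. All of that stands. It narrows the defect to a mismatch between the objective's wording and its analysis.

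Four stronger readings are tempting, and the documents do not support them:
- **The plan will call the products similar if no difference is seen.** No such rule is written. The text says 'determine if', and inspection is simply the only route left open.
- **The 20% rule is the only number.** The D-dimer and ULN cut-offs are also planned.
- **These comparisons go to the DSMB for the next-trial decision.** SAP 4.5.3 lists Tables 1.1 to 8.3 (without 7.4–7.6) and Figures 1 and 2 for the DSMB; the laboratory Tables 9–13 are not among them. Protocol 6.1 also bases conclusions on the safety objectives on TEAEs only.
- **The trial would miss a difference of 0.5 SDd 78% of the time.** That is the miss rate of a two-sided 5% test, which the plan does not run.

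It is also fair that requiring an interval inside a limit for each of the 38 measures in Table 12 would create dozens of equivalence decisions with no multiplicity plan. Such a rule should be optional and kept to a few key analytes.

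**Conclusion.** The concern holds as a mismatch. The objective promises a judgement of similarity, and the plan has no between-product limit, no within-subject FDP minus FFP difference in any shell, and no interval. Any similarity statement in the final report would rest on reading summaries and plots from 8 subjects. This does not touch the primary safety objective, and a descriptive aim would be acceptable if worded as one.

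The size is the precision left unreported: 0.69 SDd at 90% and 0.87 SDd at 95%. This assumes 8 completers (4 per sequence), roughly normal differences, no differential carryover and an SDd that the documents do not supply. Apparent agreement of means is compatible with true differences of that order.

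**What to change.** 1. In protocol 11.1.2.2 and the SAP section for Secondary Objective #2, add one Cohort 3 table. For each continuous coagulation, hematology and chemistry measure, give the within-subject FDP minus FFP difference in change from baseline with a period-adjusted 90% (or 95%) CI (2x2 crossover, 6 df). Report it at 0.5 h, at 4 h, and at 24 h, wherever protocol Table 15 / SAP Table 5 lists the time point. The 28-day visit follows the second infusion only, so it cannot provide this difference.
2. In protocol 6.2 and 6.4.2 and SAP 1.2.2 (and the matching synopsis sentence), change the objective from determining similarity to describing the difference. The exception is any key analyte for which the sponsor records a between-product limit before Cohort 3 is unblinded. For those, state similarity only if the CI lies wholly inside the limit. The choice of limits is the sponsor's.

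Cost: a small protocol and SAP amendment (protocol 11.6 requires changes to the statistical plan to be documented this way) and one added table from data already collected. No subjects, visits or samples are added. The downside is fewer claims of similarity: where SDd equals the limit, even identical products would pass only about 61% of the time.
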